In our preliminary study (unpublished) with limited sample size, we compared two different bone marrow samples (CD138 selected DNA extract vs. formalin-fixed paraffin embedded (FFPE) bone marrow clot section) from same patients (from Moffitt Cancer Center) and demonstrated that high-throughput sequencing technology by Adaptive Biotechnologies can identify the index myeloma clones (data not shown). We hypothesize that high-throughput sequencing technology using PCR on CDR3 sequences will identify minimal residual disease in myeloma patients after autologous HCT followed by panobinostat maintenance and bone marrow samples will be obtained prospectively to analyze this technology.

3 Study rationale/purpose

Optimal maintenance therapy after autologous HCT in multiple myeloma has not been defined. Based on preclinical and clinical data demonstrating anti-myeloma activity of panobinostat, we propose an open-label, trial to determine the safety and tolerability of 2 dosing schedules of panobinostat maintenance therapy in patients with multiple myeloma who underwent autologous HCT. As noted in prior maintenance therapy in myeloma, the dose of maintenance single agent is usually started at a lower dose (such as 10 mg starting dose for lenalidomide maintenance compared to 25 mg full dose in relapsed/refractory disease treatment) due primarily to (1) lower disease burden after autologous HCT and (2) limited tolerability and susceptibility to cytopenias immediately after autologous HCT. Panobinostat maintenance therapy will be initiated between 90 days and 180 days after autologous HCT at a starting dose of (a) 20 mg PO three times a week, every other week, every 4 weeks (Cohort A), or (b) 10 mg po daily x 7 days, every other week, every 4 weeks (Cohort B). Maintenance therapy will be prescribed for a maximum for 12 cycles (4 weeks x 12 cycles = 48 weeks) for both cohorts. The dose delivered to each cohort would be 60 mg per week for Cohort A and 70 mg per week for Cohort B. Long-term tolerability of each dose schedule of panobinostat

maintenance therapy after autologous HCT is unknown and the study intends to evaluate the safety and tolerability in multiple myeloma patients.

4 Study objectives

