6.1.3 Inclusion and exclusion criteria (for panobinostat maintenance)

Patients will be enrolled to the panobinostat maintenance therapy study after receiving autologous HCT. Patients must have baseline evaluations performed prior to the first dose of study drug and must meet all inclusion and exclusion criteria. Results of all baseline evaluations confirming eligibility must be reviewed by the Principal Investigator (or co-investigator) prior to enrollment of that patient. In addition, the patient must be thoroughly informed about all aspects of the study, including the study visit schedule and required evaluations and all regulatory requirements for informed consent. The written informed consent must be obtained from the patient prior to enrollment. The following criteria apply to all patients enrolled onto the study unless otherwise specified.

Inclusion criteria (for panobinostat maintenance)

1. Adult patients, age ≥ 18 years old
2. Ability to provide written informed consent obtained prior to participation in the study and any related procedures being performed
3. Histologically confirmed diagnosis of multiple myeloma
4. Meeting the criteria for symptomatic multiple myeloma (“CRAB” criteria – See **Appendix B**) before the initiation of systemic chemotherapy
5. Received high-dose melphalan (≥ 140 mg/m²) followed by autologous HCT based on the institutional guidelines and within +45 and +180 after autologous HCT at the time of panobinostat maintenance initiation.
6. Patients must have achieved at least PR prior to autologous HCT and must not have progressive disease (PD) prior to the initiation of maintenance therapy (See **Appendix C** for response criteria)
7. Patients must meet the following laboratory criteria (prior to the initiation of panobinostat maintenance):
 - ANC $\geq 1 \times 10^9$ /L
 - Hemoglobin ≥ 8 g/dl
 - Platelets $\geq 50 \times 10^9$ /L (without transfusion support)
 - Creatinine clearance ≥ 40 ml/min or serum creatinine $\leq 2.5 \times$ ULN
 - AST and ALT $\leq 2.5 \times$ ULN
 - Serum bilirubin $\leq 1.5 \times$ ULN
 - Albumin > 3.0 g/dl
 - Clinically euthyroid. Note: Patients are permitted to receive thyroid hormone supplements to treat underlying hypothyroidism.

8. Baseline (pre-HCT) MUGA or ECHO must demonstrate LVEF \geq the LLN of the institutional normal.
9. ECOG Performance Status of ≤ 2 or Karnofsky performance status $\geq 70\%$ (See **Appendix D** and **Appendix E**)

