7.1 Investigational therapy

[figure not shown]
Screening consents will be signed prior to autologous HCT to access pre-HCT stem cell graft, bone marrow and peripheral blood samples for the correlative studies. Patients will be enrolled after autologous HCT. Patients will be initiated on panobinostat maintenance therapy between day +90 and +180 after autologous HCT. Patients who develop disease progression before day +90 after autologous HCT will be ineligible for the study.

Panobinostat (also known as LBH589) will be provided by Novartis. Oral panobinostat will be supplied as 5-mg, 10-mg, 15-mg or 20-mg pink/opaque-colored, hard gelatin capsules.

Medication labels will comply with US legal requirements and be printed in English. They will supply no information about the patient. The storage conditions for study drug will be described on the medication label.

During the study, panobinostat will be administered orally as either (1) once daily dose of 20 mg (1 x 20-mg capsule) three times per week, every other week, of a 28-day schedule (Cohort A), or (2) once daily dose of 10 mg (1 x 10-mg capsule) daily x 7 days, every other week, of a 28-day schedule (Cohort B). Both cohorts will receive a maximum of 12 cycles of maintenance therapy (Figure 7-1).

Figure 7-1. Panobinostat maintenance schedule

Patients should be instructed to take their once-a-day oral dose of panobinostat at the same time each morning. Each dose of panobinostat should be taken with an 8 oz / 240 ml glass of water. Patients should be instructed to swallow the capsules whole and not chew them. Patients must avoid grapefruit or grapefruit juice and seville (sour) oranges during the entire study.

If a subject experiences toxicity, the dose of panobinostat will be reduced to one level lower (Table 7-1) and maintained at this level for all subsequent cycles unless further toxicities occur. Panobinostat dose modifications will be made according to the toxicity grading. Once a subject's dose of panobinostat is reduced, then that dose will be the maximal dose administered.

On the days of ECG monitoring, drug administration should be supervised by study center personnel and administration time should be recorded.

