7.5.4 Pneumococcal-13 conjugate vaccine administration (standard of care)

As a standard of care, pneumococcal-13 conjugate vaccine (Prevnar-13™) will be administered to many of autologous HCT recipients at around day +90 (prior to the initiation of maintenance therapy).

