8.1 Visit schedule

Table 8-1 Evaluation and visit schedule

	Pre-HCT (Screening, not required)	Prior to maintenance (Enrollment: +45 to +180) [§]	Cycle #1 (start between +90 and +180)	Cycle #2****	Cycle #3****	Cycle #4****	Cycle #5****	Cycle #6****	Cycle #7****	Cycle #8****	Cycle #9****	Cycle #10*** *	Cycle #11*** *	Cycle #12*** *	End of study visit (4 weeks (± 14 days) follow up after the first dose of cycle #12)
Consent	X ⁺	X													
Enrollment		X													
H&P (SOC)		X	X ^{SS§}	X	X	X	X	X	X	X	X	X	X	X	X
Concomitant medications		X													
Toxicity (adverse event (AE)) assessment ^{SS}			X	X	X	X	X	X	X	X	X	X	X	X	X
Vital signs (SOC)		X ⁺⁺	X	X	X	X	X	X	X	X	X	X	X	X	X
EKG		X	X [*]	X ^{**}	X ^{**}	X ^{**}									
CBC and CMP (SOC)		X	X ^{***}	X ^{***}	X	X	X	X	X	X	X	X	X	X	X
PT/INR/PTT		X			X			X							X
LDH, cholesterol panel, GGT, uric acid		X													
Urinalysis		X													X
TSH, free T4		X													X
Serum pregnancy test ⁺⁺⁺		X	X	X	X	X	X	X	X	X	X	X	X	X	
SPEP, UPEP and serum free		X			X			X			X			X	

Confidential

light chains (SOC)															
Pneumococcal-13 conjugate vaccine (at around day +90 – SOC)		X [#]													
Peripheral blood research samples	X	X	X ^{****}	X	X			X			X				X
Bone marrow research samples	X [@]	X													X
Stem cell graft research samples	X														

*Single 12 lead EKG will be performed for pre-dose and 3 hours (± 15 minutes) post-dose on days 1 and 5 of cycle 1. A total of 4 EKGs during cycle 1 will be performed.
 **Single 12 lead EKG will be performed for pre-dose on day 1 of cycle 2 and beyond at each cycle (at least through cycle 4). If no significant QTcF prolongation is noted during the first cycle, then QTc monitoring is no longer required beyond cycle 4 (and may be performed at the investigator’s discretion). One EKG per cycle from cycle 2 to 4 (minimum).
 ***CBC to be performed weekly during cycle #1 and #2. CBC/CMP will also be performed on day 5 of cycle 1.
 ****Window to start cycles #2 to #12 would be ±7 days from the planned first day of each cycle.
 + Screening consent for research samples (bone marrow, peripheral blood and stem cell graft)
 ++ Height will be measured at screening visit prior to starting panobinostat maintenance therapy
 +++ Only for women of child bearing potential
 ++++ Peripheral blood research samples will be also collected on day 5 of cycle 1.

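### Inclusion criterion 5 allows maintenance to start from day +45 after transplant, while section 3, section 7.1 and Table 8-1 set the first dose at day +90 or later

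*Combined protocol and SAP*

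**What the plan says.** The protocol gives the timing of maintenance relative to autologous transplant in several places.

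- **Section 6.1.3, inclusion criterion 5:** the patient must be "within +45 and +180 after autologous HCT at the time of panobinostat maintenance initiation". The event named is the start of maintenance.
- **Section 3:** "Panobinostat maintenance therapy will be initiated between 90 days and 180 days after autologous HCT".
- **Section 7.1:** "Patients will be initiated on panobinostat maintenance therapy between day +90 and +180 after autologous HCT". The same paragraph adds: "Patients who develop disease progression before day +90 after autologous HCT will be ineligible for the study".
- **Section 8.1, Table 8-1, pre-maintenance column:** "Enrollment: +45 to +180". The event here is enrollment.
- **Section 8.1, Table 8-1, Cycle 1 column:** "start between +90 and +180".
- **Section 7.5.4:** the pneumococcal vaccine is given to many recipients "at around day +90 (prior to the initiation of maintenance therapy").

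**The concern.** Criterion 5 and the treatment sections give different lower bounds for the same event, the first dose of panobinostat. Criterion 5 is also the only numbered eligibility item that sets days since transplant. A site screening from the numbered list would accept a start on day +60, and that start would breach section 7.1 and Table 8-1.

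Tolerability is the primary objective, and section 3 gives susceptibility to cytopenias soon after transplant as one reason for a reduced maintenance dose. Time since transplant at first dose is therefore a relevant design condition, although it is not part of the endpoint definition. With 15 patients per cohort, a few early starts would be noticeable. An early start would also fall before day +90, the point up to which section 7.1 treats progression as making a patient ineligible. It would usually come before the vaccine as well, which feeds only the exploratory immune objectives in section 4.2.

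**Working it through.** No power or alpha figure is involved, so the check is a comparison of the stated windows.

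| Source | Event | Window (days after transplant) |
|---|---|---|
| Criterion 5, section 6.1.3 | Maintenance initiation | +45 to +180 |
| Section 3 | Maintenance initiation | +90 to +180 |
| Section 7.1 | Maintenance initiation | +90 to +180 |
| Table 8-1, Cycle 1 column | Cycle 1 start | +90 to +180 |
| Table 8-1, pre-maintenance column | Enrollment | +45 to +180 |

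Three statements agree on day +90 for the first dose. The figure of +45 appears elsewhere only for enrollment. A misplaced anchor in criterion 5 is the most likely explanation, though the protocol does not say so.

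**Size of the conflict, counting both end days:**
- Start days admitted by criterion 5: 180 − 45 + 1 = 136.
- Start days admitted by the treatment sections: 180 − 90 + 1 = 91.
- Conflict: 136 − 91 = 45 days (+45 to +89), and 45/136 = 33.1%.

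Counting intervals instead gives 180 − 45 = 135 and 180 − 90 = 90. The difference is again 45 days, and 45/135 = 33.3%.

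**Do other criteria supply a day +90 floor?**
- Exclusion 8 (section 6.1.3) requires more than 4 weeks since chemotherapy, which is 28 days. By day +45 after high-dose melphalan that has passed. The item also requires recovery from side effects, but it sets no day.
- Criterion 6 bars progression before maintenance starts, and criterion 7 sets blood count and organ function limits. Neither sets a day.
- The section 7.1 progression rule fits a day +90 floor, because a patient dosed on day +60 could still progress before day +90 and become ineligible while on treatment. It sits outside the numbered criteria and does not itself prohibit an earlier dose.

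**The reverse gap.** Because criterion 5 speaks only of initiation, the numbered criteria contain no enrollment window. A patient enrolled on day +30 and first dosed on day +95 would meet criterion 5 yet fall outside the enrollment column of Table 8-1.

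**Effect on the statistics.** Section 13.1 states 95% confidence interval widths of 0.356, 0.438, 0.487, 0.514 and 0.522 for proportions of 0.9, 0.8, 0.7, 0.6 and 0.5. The Clopper-Pearson width is the 0.975 quantile of Beta(np + 1, n − np) minus the 0.025 quantile of Beta(np, n − np + 1). With n = 15 this gives 0.356, 0.438, 0.487, 0.514 and 0.522, matching the plan. None of these depends on the start day, and neither does the completion endpoint in section 13.1.3.

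**The case against.** The strongest reply is that all the rules can be met together. An eligibility criterion is a necessary condition and does not instruct anyone to dose. A site that follows section 7.1 and Table 8-1 will never dose before day +90 and will never breach criterion 5. On this view criterion 5 is merely loose: it forces no violation and wrongly excludes nobody. That is correct as far as it goes, and it is why the point is minor. It also leaves the +45 bound in criterion 5 with no function, and it does not help a site that screens from the numbered list.

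Four further objections bear on emphasis:

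- The progression sentence in section 7.1 is an ineligibility rule and not a scheduled day +90 assessment. Criterion 6 bars progression before maintenance whatever the start day. Both points stand.
- The vaccine timing is approximate. The footnote to Table 8-1 only advises it, and vaccination is not a precondition for dosing. This stands, so the vaccine is supporting context only.
- One third is a share of calendar days. Nothing in the documents indicates that any patient would start before day +90. This stands, and the figure describes the width of the conflict only.
- Criteria 6 and 7 and the recovery clause of exclusion 8 limit the risk of an early start. They do, but they do not replace a minimum day.

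**Conclusion.** The concern holds, as a minor error in an operative eligibility rule. Criterion 5 contradicts section 3, section 7.1 and the Cycle 1 column of Table 8-1 for any first dose on days +45 to +89.

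The conclusion rests on the current text alone. The one inference is that day +90 is the intended lower bound for dosing, supported by three concordant statements and by the separate enrollment window in Table 8-1. The contradiction exists whichever bound was intended; the inference decides only which text should change. How many patients might start early, and what that would do to tolerability, cannot be determined from the documents.

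**What to change.** Reword the timing clause of criterion 5 along these lines: *enrollment on day +45 to +180, and first panobinostat dose on day +90 to +180, after autologous transplant*. This agrees with section 3, section 7.1 and both columns of Table 8-1, and it puts the enrollment window into the numbered criteria. It is a one-sentence amendment with no effect on sample size, visits or analysis.

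If a start from day +45 is intended instead, section 3, section 7.1 (including the day +90 progression rule), the Cycle 1 column of Table 8-1 and the vaccine timing in section 7.5.4 all need to change. That alternative alters the treatment schedule and goes beyond a wording correction.

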7.1 Investigational therapy

[figure not shown]
Screening consents will be signed prior to autologous HCT to access pre-HCT stem cell graft, bone marrow and peripheral blood samples for the correlative studies. Patients will be enrolled after autologous HCT. Patients will be initiated on panobinostat maintenance therapy between day +90 and +180 after autologous HCT. Patients who develop disease progression before day +90 after autologous HCT will be ineligible for the study.

Panobinostat (also known as LBH589) will be provided by Novartis. Oral panobinostat will be supplied as 5-mg, 10-mg, 15-mg or 20-mg pink/opaque-colored, hard gelatin capsules.

Medication labels will comply with US legal requirements and be printed in English. They will supply no information about the patient. The storage conditions for study drug will be described on the medication label.

During the study, panobinostat will be administered orally as either (1) once daily dose of 20 mg (1 x 20-mg capsule) three times per week, every other week, of a 28-day schedule (Cohort A), or (2) once daily dose of 10 mg (1 x 10-mg capsule) daily x 7 days, every other week, of a 28-day schedule (Cohort B). Both cohorts will receive a maximum of 12 cycles of maintenance therapy (Figure 7-1).

Figure 7-1. Panobinostat maintenance schedule

Patients should be instructed to take their once-a-day oral dose of panobinostat at the same time each morning. Each dose of panobinostat should be taken with an 8 oz / 240 ml glass of water. Patients should be instructed to swallow the capsules whole and not chew them. Patients must avoid grapefruit or grapefruit juice and seville (sour) oranges during the entire study.

If a subject experiences toxicity, the dose of panobinostat will be reduced to one level lower (Table 7-1) and maintained at this level for all subsequent cycles unless further toxicities occur. Panobinostat dose modifications will be made according to the toxicity grading. Once a subject's dose of panobinostat is reduced, then that dose will be the maximal dose administered.

On the days of ECG monitoring, drug administration should be supervised by study center personnel and administration time should be recorded.

If the patient forgets to take his/her dose during the morning on scheduled treatment day (i.e., day 1 of each cycle), then he/she should take panobinostat (LBH589) on that same day within 12 hours after the missed dose if possible. After more than 12 hours, that day's dose should be withheld, and the patient should wait to take panobinostat (LBH589) until the next scheduled treatment day (i.e., patients should be instructed not to try to make-up the missed dose after 12 hours). The patient should then continue treatment with the original dosing schedule.

The investigator should instruct the patient to take the study drug exactly as prescribed (promote compliance). All dosages prescribed and dispensed to the patient and all dose changes during the study should be recorded.

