4.2 Secondary

- To evaluate the complete response rate to panobinostat maintenance therapy after autologous HCT.
- To determine the 2-year PFS and OS of autologous HCT followed by panobinostat maintenance therapy in patients with multiple myeloma.
- **Exploratory secondary objectives:**
 - To evaluate histone acetylation (H3 and/or H4) of peripheral blood mononuclear cells
 - To isolate and identify clonotypic B cell progenitors in multiple myeloma patients from the bone marrow, peripheral blood and stem cell grafts.
 - To evaluate T-cell immune response against known myeloma tumor associated antigens while on panobinostat maintenance.
 - To evaluate humoral immunity against pneumococcal serotypes included in the standard of care heptavalent pneumococcal conjugate vaccine, and to assess cellular immune responses against CRM adjuvant found in the heptavalent pneumococcal conjugate vaccine.
 - To evaluate minimal residual disease (MRD) after autologous HCT followed by panobinostat maintenance therapy using flow cytometry
 - To evaluate MRD after autologous HCT followed by panobinostat maintenance therapy using multiplex PCR for CDR3 sequences

5 Overall study design

This is an open-label trial to determine the safety and tolerability of 2 different dosing schedules of single agent panobinostat maintenance therapy in patients with multiple myeloma who underwent high-dose melphalan followed by autologous HCT in patients with multiple myeloma. It is unknown whether the toxicity profile of panobinostat will be accentuated in patients after autologous HCT in the setting of maintenance therapy, hence the dose chosen for maintenance therapy is lower than MTD dosing or other phase 2 studies. There are 2 dosing schedules evaluated in this protocol in order to assess optimal tolerable schedule for panobinostat maintenance therapy after autologous HCT. As secondary

objectives, we will evaluate response after completion of treatment, and 2-year PFS and OS. As correlative studies, we plan to evaluate MRD, and to assess clonotypic B cells following an autologous HCT. We also plan to evaluate T effector immune response after autologous HCT while on panobinostat maintenance therapy.

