13.1 Statistical methods and data analysis

This is an open label study of 2 different panobinostat maintenance dosing schedules after autologous HCT in patients with multiple myeloma. There are 2 cohorts and patients will be enrolled sequentially to cohort A, then to cohort B. The sample size is 30 patients for this trial (15 for each cohort). We expect that at least 2/3 of each cohort will complete 12 cycles of maintenance panobinostat (regardless of dose modification) and will be evaluable for the primary endpoint. The widths of 95% confidence interval (CI) are 0.356, 0.438, 0.487, 0.514, and 0.522 when the proportions of patients tolerating 12 cycles of maintenance are 0.9, 0.8, 0.7, 0.6, and 0.5, respectively.

A patient who withdraws from the study due to reasons other than death, disease progression or toxicity will be replaced and is considered as non-evaluable for primary endpoint. The proportion of patients tolerating the therapy will be reported with 95% CI. All 30 patients are eligible for secondary endpoints. We will compute the overall response rates before the transplant, after autologous HCT, and after the completion of maintenance therapy, and at best response. The OS and PFS will be estimated using the Kaplan-Meier method. We will also report the incidences of all grades and grade ≥ 3 toxicities. The two-sided 95% CIs for

proportion, and OS and PFS will be computed using the Clopper-Pearson method and the Greenwood formula, respectively. In addition, the frequency of B cell precursor as well as other cell subsets, and their 95% CI will be evaluated using t-distribution. If data do not meet normality assumption, the power transformation (e.g., log-transformation) will be conducted. Those patients who are not in CR before the transplant would be most suitable for T-effector activity analysis. This will be examined by the paired t-test or the Wilcoxon signed-rank test, depending on the data distribution.

Relative dose intensity (RDI) represents the ratio of the amount of a drug actually delivered [actual dose intensity (DI)] to the amount planned (planned DI). The purpose of calculating RDI is to evaluate whether the planned DI of a chemotherapy treatment was actually achieved which may suggest the feasibility of planned treatment regimen. There are multitude of reports demonstrating a correlation between RDI and survival in cancer treatment.

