13.1.4 Secondary objective and hypothesis

The secondary objectives of the study are to evaluate following parameters in patients who receive panobinostat maintenance therapy after autologous HCT: overall response rate, best response rate, 2-year PFS and 2-year OS. The exploratory secondary objectives include evaluation of minimal residual disease, frequency of B cell precursors and immune subsets, protein acetylation, and immune response against pneumococcal vaccines and CRM. The association of minimal residual disease, B cell precursors, and immune response with response, PFS and OS will be evaluated using the Cox proportional hazards regression model.

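### The 2-year PFS and OS objective covers the strategy from transplant, but treated patients must be event-free at first dose and no time zero is set; counting from HCT would bias the rates upward

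*Combined protocol and SAP*

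**What the plan says.** The secondary objective in Section 4.2 is "To determine the 2-year PFS and OS of autologous HCT followed by panobinostat maintenance therapy in patients with multiple myeloma". Section 13.1.4 words the same endpoints differently, as evaluated "in patients who receive panobinostat maintenance therapy after autologous HCT: overall response rate, best response rate, 2-year PFS and 2-year OS".

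Section 7.1 states "Patients will be enrolled after autologous HCT" and also "Patients who develop disease progression before day +90 after autologous HCT will be ineligible for the study". Inclusion criterion 6 in Section 6.1.3 adds that a patient "must not have progressive disease (PD) prior to the initiation of maintenance therapy".

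For the analysis, Section 13.1 says "The OS and PFS will be estimated using the Kaplan-Meier method", with Greenwood intervals, and "All 30 patients are eligible for secondary endpoints".

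No section defines PFS or OS, says whether time runs from HCT, enrolment or first dose, or mentions a landmark or delayed entry. The start window is also inconsistent. Sections 3 and 7.1 and Table 8-1 start maintenance between day +90 and day +180, while inclusion criterion 5 in Section 6.1.3 has patients between day +45 and day +180 at initiation.

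**The concern.** The objective describes a strategy that begins at transplant, but the treated sample consists of people who have already come through the first part of it without progression or death. A Kaplan-Meier curve started at HCT would count each of them as at risk during weeks in which an event would have kept them out. Early failures never enter the denominator, so the curve starts with guaranteed event-free time. The error runs in one direction, does not shrink with more patients or longer follow-up, and is not reflected in a Greenwood interval.

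Starting the clock at first dose avoids this, but then answers a different question from Section 4.2. Two analysts following the protocol could therefore report different 2-year rates from the same 30 patients. The Cox models for PFS and OS in Section 13.1.4 lack a time origin for the same reason.

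**Working it through.** **The plan's own figures.** The only computed design figures are the exact 95% interval widths for the 12-cycle completion rate with 15 patients: 0.356, 0.438, 0.487, 0.514 and 0.522. Clopper-Pearson limits reproduce them (0.3561, 0.4376, 0.4868, 0.5138, 0.5224). They concern the primary endpoint. No target, null rate or precision is given for 2-year PFS or OS.

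**Inputs for illustration.** From Section 1.1.1: median PFS of 23 and 41 months (IFM 05-02, placebo and lenalidomide) and 3-year OS of 80% and 88% (CALGB 100104, placebo and lenalidomide). Start days are 45, 90 and 180; with 30.4375 days per month these are 1.48, 2.96 and 5.91 months. The constant hazard is an assumption.

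**Formulas.** S(t) = exp(−λt), with λ = ln 2 / median for PFS and λ = −ln(3-year OS) / 36 for OS. Among patients required to be event-free at month m, ordinary Kaplan-Meier from HCT estimates S(24)/S(m). The bias against an unselected transplant cohort is S(24)/S(m) − S(24).

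**Example.** For a median of 23 months, λ = 0.6931/23 = 0.03014. S(24) = exp(−0.723) = 0.485. At day 90, S(2.96) = exp(−0.0891) = 0.915, and 0.485/0.915 = 0.530, or +4.5 points.

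| Assumed rate | S(24) | Start day 45 | Start day 90 | Start day 180 |
|---|---|---|---|---|
| PFS, median 23 months | 48.5% | 50.7% (+2.2) | 53.0% (+4.5) | 58.0% (+9.5) |
| PFS, median 41 months | 66.6% | 68.3% (+1.7) | 70.1% (+3.4) | 73.7% (+7.0) |
| OS, 80% at 3 years | 86.2% | 87.0% (+0.8) | 87.8% (+1.6) | 89.4% (+3.2) |
| OS, 88% at 3 years | 91.8% | 92.3% (+0.5) | 92.8% (+1.0) | 93.8% (+1.9) |

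Differences are taken before rounding.

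**Comparison of time origins.** In a simulation of 1,000,000 patients per scenario, with first dose uniform over day 90 to 180 and no censoring, 2-year PFS was:

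| Estimate | Median 23 months | Median 41 months |
|---|---|---|
| Unselected, from HCT | 48.5% | 66.6% |
| Ordinary Kaplan-Meier from HCT, treated patients | 55.4% | 71.8% |
| Kaplan-Meier from HCT with delayed entry | 53.0% | 70.1% |
| Kaplan-Meier from first dose | 48.5% | 66.6% |

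Delayed entry gives survival to 24 months conditional on being event-free at day 90, not the unconditional rate from HCT. The first-dose figures equal the unselected ones only because the assumed hazard is constant; in general they are a different quantity.

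**Sensitivity to the early hazard.** The bias can be written S(24) × [1/S(m) − 1], so it depends on how many events fall before entry. Halving the hazard before entry while holding S(24) fixed halves the exponent in S(m), which has the same effect as halving m. The PFS bias for day 90 to 180 is then 2.2 to 4.5 points (median 23 months) or 1.7 to 3.4 points (median 41 months).

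**Sampling error for scale.** With 30 patients, the approximate 95% half-width is 1.96 × √(p(1−p)/30): 17.9 points at p = 0.5 and 16.4 at p = 0.7.

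**The case against.** The strongest reply is that nothing in the protocol starts the clock at HCT. Enrolment follows transplant, so enrolment or first dose is an available origin, and Section 13.1.4 already restricts the endpoints to patients who receive maintenance. From first dose, this bias is zero. That stands. A reader might infer that the planned rates are certainly inflated by three to six guaranteed months, but the documents do not support so firm a claim. Time zero is missing, and under inclusion criterion 5 the guaranteed time could be as short as about 1.5 months.

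The guarantee is also shown only for treated patients. Table 8-1 allows enrolment from day +45 with cycle 1 from day +90. The protocol does not say whether someone who dies or progresses between enrolment and first dose stays among the 30.

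A reader might further infer that the guaranteed months would be presented as panobinostat benefit against Tables 1-1 to 1-3. No such comparison is planned. Section 1.1.1 says the lenalidomide patients were randomised after HCT, and the documents do not give the time origins of those rates. The cited medians therefore only set a plausible range here.

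Finally, the bias is smaller than the sampling error, and the OS effect is small. Both are true. But the interval expresses sampling error and would not show this shift. Nor does the missing origin rescue the plan: from HCT the estimate is biased for the stated objective, and from first dose it is not an estimate of that objective.

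**Conclusion.** The point holds in conditional form. The objective in Section 4.2, the eligibility rules and the plain Kaplan-Meier plan do not fit together, and the objective's wording points the analyst towards the biased origin. If time is counted from HCT, 2-year PFS is overstated by about 3.4 to 9.5 points and OS by about 1 to 3 points for starts at day +90 to +180. For a day +45 start the figures are about 2 points and under 1 point. These sizes rest on a constant hazard, on borrowed rates and on every analysed patient being event-free at first dose; a lower early hazard makes them smaller. It would be wrong to treat PFS and OS as equally affected.

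The endpoints are secondary and descriptive, with no test or target. The completion-rate endpoint and the sample size are unaffected. The change is worth making before results are known, because afterwards the choice of origin could follow the more favourable figure.

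**What to change.** In Sections 4.2, 13.1 and 13.1.4, define PFS and OS, with their events, from the first panobinostat dose, and reword the objective as 2-year PFS and OS from the start of maintenance. State how patients enrolled but never dosed are handled. Use the same origin in the Cox models.

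If a figure from HCT is also wanted, estimate it with delayed entry at first dose and label it as conditional on being alive and progression-free at entry. The text should say that this cannot recover the unconditional rate from HCT.

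Reconcile the start windows in Section 6.1.3 (day +45) and in Sections 3 and 7.1 and Table 8-1 (day +90).

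The cost is mostly wording. The 2-year figure will be lower than one counted from HCT. Reaching two years from first dose takes up to about 6 months more follow-up than two years from HCT (180/30.4375 = 5.9 months), or else some patients are censored earlier. Table 8-1 ends about 4 weeks after the first dose of cycle 12, so survival follow-up to two years has to be scheduled under either origin.
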